8.4.1.2. Demographic and Other Baseline Characteristics

8.4.1.2.1. Demographics:

Continuous: age, height, weight, Body Mass Index (BMI);

Categorical: age categorized as ≤ 64 years versus ≥ 65 years, and ≤ 19 , 20–29, 30–39, 40–49,

50–59, 60–69, \geq 70, gender, race, ethnicity, country and region defined as America- AM, Europe -EU and Asia Pacific - AP

- BMI will be calculated as weight at screening (kg) / {height at screening (m)}² and reported to 1dp.

Table 2: Demographic and Baseline Characteristics

Category	Item	Type of Data	Definition/Breakdown
Demography	Gender	Binary	Male, Female
	Race	Categorized	
 1. White 2. Black or African American 3. Asian – Japanese 4. Asian - Not Japanese 5. American Indian or Alaska Native 6. Native Hawaiian or Pacific Islander 7. Not Reported 8. Other
	Age (year)	Continuous	
		Categorized	\leq 19, 20–29, 30–39, 40–49, 50–59, 60–69, \geq 70
		Categorized (binary)	<65 , ≥ 65
	Height (cm)	Continuous	
	Body weight (kg)	Continuous	
	BMI	Continuous	Weight at screening (kg) / {height at screening (m)} ²
	Country	Categorized	United States, Canada, Germany, Italy, Switzerland, Japan, South Korea
	Region	Categorized	
 1. America-AM 2. Europe -EU 3. Asia Pacific - AP
	Ethnicity	Categorized	
 1. Hispanic or Latino 2. Not Hispanic or Latino 3. Not Reported 4. Unknown

8.4.1.2.2. ALS History:

Continuous:

- (1) Disease Duration from Onset of Symptoms (years) and from ALS Diagnosis (years),
- (2) ALSFRS-R score at screening,
- (3) ALSFRS-R at Baseline,

Categorical:

- (1) ALSFRS-R Deterioration Rate of (-1,-2) or (-3,-4),
- (2) Disease duration from Onset of Symptoms categorized at <1 year vs \geq 1 year and from Onset of ALS Diagnosis categorized at <1 year vs \geq 1 year,
- (3) Initial symptom categorized as 'Bulbar onset' or 'Limb onset',
- (4) ALS Diagnosis categorized 'Sporadic' or 'Familial',
- (5) Categorical El Escorial revised Diagnostic,
- (6) Concomitant use of riluzole 'Present' or 'Absent',
- (7) Previous use of AMX0035 'Present' or 'Absent',
- (8) Concomitant use of AMX0035 'Present' or 'Absent',

Table 3 : ALS History Parameters

Category	Item	Type of Data	Definition/Breakdown
ALS Disease History	Disease duration from Onset of Symptoms to Screening (year)	Continuous	(Date of Screening - Date of Onset of Symptoms*)/365.25
	Categorized (binary)	< 1 year, \geq 1 year	
	Disease duration from Diagnosis to Screening (year)	Continuous	(Date of Screening - Date of Diagnosis*)/365.25
		Categorized (binary)	< 1 year, \geq 1 year
	ALSFRS-R score at screening	Continuous	At Screening
	ALSFRS-R score at baseline	Continuous	At Baseline
	ALSFRS-R Deterioration Rate	Categorized	(-1,-2) , (-3,-4)
	Initial symptom	Binary	Bulbar onset, limb onset
	ALS diagnosis	Binary	Sporadic, Familial

	El Escorial revised Airlie House Diagnostic Criteria	Binary	Definite ALS, Probable ALS, Probable - Laboratory-Supported ALS, Possible ALS
	Concomitant use of riluzole	Binary	Present, Absent
	Previous use of AMX0035	Binary	Present, Absent
	Concomitant use of AMX0035	Binary	Present, Absent

*If Date of Onset of Symptoms and Date of Diagnosis are incomplete, the following steps will be considered. If the above date is completely missing, the corresponding duration will not be derived. If the start month is missing, then the first month will be used. If the start day is missing, then the first day will be used.

8.4.1.3. Medical History

Medical history data will be coded using the Medical Dictionary for Regulatory Activities (MedDRA version 23.0).

8.4.1.4. Prior and Concomitant Medication

Definition of prior medications and concomitant medications in the protocol

At screening, subjects will be asked what medications (including riluzole) they have taken during the last 3 months prior to screening visit and will be recorded in the subject's source documents and eCRF as prior medication.

Concomitant medication is defined as any medication, other than the study drug, which is taken from screening up to week 48 Visit, including prescription, herbal and over-the-counter medications. All concomitant medications taken while the subject is participating in the study will be recorded in the eCRF.

All medications will be classified using the Anatomical Therapeutic Chemical (ATC) classification codes and preferred drug names from the World Health Organization Drug Dictionary (WHO-DD, version from September 2022).

Rules to determine prior medications and concomitant medications

Medications with a stop date before the first date of study drug dosing will be considered prior medications. Medications with start date or stop date on or after the first date of study drug dosing or ongoing up to week 48 will be considered concomitant medications. .

If the medication start date is incomplete, then it will be imputed as follows for the purpose of determining concomitant use:

- If the start date is completely missing, the start date will be equal to the first dose date. However, if the stop date is not missing and is before the first dose date, then the stop date will be used instead.
- If the start day is missing, the first day of the month will be used.
- If the start day and month are missing, then the first day of the first month (January) will be used.

If the medication stop date is partial, then it will be imputed as follows for the purpose of determining concomitant use:

- If the stop date is completely missing and the medication is not ongoing, the stop date will be equal to the last dose date or date of completion/withdrawal, whichever is the latest.
- If the stop day is missing, the last day of the month will be used.
- If the stop day and month are missing, then the last day of the last month (December) will be used.

8.4.1.5. Exposure to Study Medication and Compliance

Exposure

Study medication exposure in days will be calculated for each subject using the following:

Exposure duration (days)=Date of last study drug up-to week 48 – date of first study drug + 1

If the date of first study drug dose or the date of the last study drug dose up-to week 48 cannot be determined, then the duration calculation will not be completed. Interruptions and compliance will not be considered for the duration of exposure.

The total exposure in person years will be calculated as the sum of duration of exposure to study treatment over all patients in days divided by 365.25.

Treatment Compliance

Treatment compliance will be calculated for each subject using the following:

Treatment compliance(%)

$$\frac{\text{Exposure duration} - \text{count of study medication days missed} + \text{count of additional study medication}}{\text{Exposure duration}} \times 100\%$$

The #count of study medication missed and additional study medication are collected by CRF visit.

Treatment compliance will be calculated using the formula below and reported to 1dp.

Date switched to PEG/RIG administration

If the date of switched to PEG/RIG administration is partial, then it will be imputed as follows:

- If the switched day is missing, the first day of the month will be used.
- If the switched day and month are missing, then the first day of the first month (January) will be used.

If the imputation date is earlier than date of the first study drug, the imputation date will be same as date of the first study drug.

8.4.2. Efficacy Measures

8.4.2.1. Combined Assessment of Function and Survival Score (CAFS)

CAFS ranks patients' clinical outcomes based on survival time and change in the ALSFRS-R score¹⁰.

CAFS Scoring:

To calculate a patient's CAFS, each patient is compared individually to all other patients in the study. The summary score for each patient is the sum of the comparisons (1, 0, 1) against all other patients (Figure 2). For each pairwise comparison of patients, the patient who fares better earns a point, and the one who fares worse loses a point. In the case of a tie, no points are added or subtracted. If both participants die, the one surviving longer fared better; if only one survives then that patient fared better; and if both participants survive, the one with the smaller decline in ALSFRS-R from baseline to week 48 fared better. If a participant discontinues early or ALSFRS-R at week 48 are missing, the participant will be treated as alive at week 48 and the ALSFRS-R at week 48 will be imputed missing using multiple imputation under missing mechanism assumption.

CAFS Ranking:

Next, patients' summary scores are ranked (Figure 3). In general, the ranking has the following characteristics:

- (1) The first patient who dies will have the lowest score and is ranked the lowest;
- (2) the last to die is ranked above all others who die;

- (3) Among survivors, the patient with the greatest decline in ALSFRS-R is ranked just above the last patient who died;
- (4) The surviving patients with the least decline in ALSFRS-R is ranked highest.

[REDACTED]

[REDACTED]

The average rank score is then calculated for each treatment group. A higher mean rank score indicates that participants in that treatment group, on average, fared better.

Figure 2: [REDACTED]

8.4.2.2. %Slow Vital Capacity (%SVC) Change from Baseline at week 4, 8, 12, 24, 36 and 48

SVC measurements will be conducted in clinic at around the same time of day where possible with the subject in sitting upright position. Subjects should make at least 3 attempts to generate acceptable and reproducible SVC data. If subjects cannot complete all three attempts due to disease progression or other reasons, it will not be considered a protocol deviation. The best value will be selected and will be recorded in the eCRF.

8.4.2.3. ALSAQ40 Change from Baseline at week 24 and 48

The ALSAQ is a patient self-report health status PRO (Patient Reported Outcome). The ALSAQ is specifically used to measure the subjective well-being of patients with ALS.

There are 40 items in the long form ALSAQ-40, with 5 discrete scales:

- Physical mobility (10 items)
- Activities of daily living and independence (10 items)
- Eating and drinking (3 items)
- Communication (7 items)
- Emotional reactions (10 items)

Patients are asked to think about the difficulties they may have experienced during the last two weeks (e.g. I have found it difficult to feed myself). Patients are asked to indicate the frequency of each event by selecting one of 5 options (Likert scale):

never/rarely/sometimes/often/always or cannot do at all.

The Investigator (or sub-investigator) will evaluate subjects using the ALSAQ40 and rater scores will be collected at the time points described in Table 1. The evaluation results, together with the dates of evaluation, will be recorded in the eCRF. The ALSAQ-40 total score will be derived as the sum of 40 items.

8.4.2.4. Time to death, tracheostomy, or permanent assisted mechanical ventilation:

On Day 1 of study drug treatment through EOT/ET, the Investigator (or subinvestigator) will investigate the presence or absence of the following events:

- Death
- Tracheostomy
- Permanent assisted mechanical ventilation (≥ 23 hours/day)

If any of the events are present, the following will be recorded in the eCRF; the date of the

event and EOS date will be investigated. When a subject discontinues the study, study sites must follow-up with phone calls at the time points described in Table 1. The evaluation results, together with the dates of the evaluation, will be recorded in the eCRF.

The time to first occurrence of death, tracheostomy, or permanent assisted mechanical ventilation (defined on EMA Guideline on clinical investigation of medicinal products for the treatment of amyotrophic lateral sclerosis, 1 November 2015) will be derived as follow:

- In case the event mentioned above is observed any time up to the last observed visit date when week 48 data base is locked, then the time variable for each subjects will be calculated as:
 - The date of the event - Randomization date +1
- In case the event is not observed until the last observed visit date when week 48 data base is locked, a right censoring will be performed for each subject at the last observed date of treatment. the time variable for each subjects will be calculated as:
 - Last observed Date - Randomization date +1
- Indicator (censoring) variable will be created to indicate an event (0) if the event was observed or censoring (1) if the event is not observed and at week 48 data base lock the subjects was either discontinued or is ongoing.
-

8.4.2.5. Time to death or permanent assisted mechanical ventilation:

Variable derivation will be performed similar to the time to death, tracheostomy, or permanent assisted mechanical ventilation.

8.4.2.6. Time to death:

Variable derivation will be performed similar to the time to death, tracheostomy, or permanent assisted mechanical ventilation.

8.4.2.7. Changes from baseline in ALSFRS-R score at Weeks 4, 8, 12, 24, 36, and 48

ALSFRS-R is a questionnaire used to measure the impact of ALS that is evaluated by the Investigator. The scale measures the subjects' physical function across 12 activities of daily living. The date of the evaluation along with the results will be recoded on the eCRF with respect to "4 Handwriting" and "5 eating motion," the results for the dominant hand (the hand used in daily life at the time of screening) will be recorded.

- ALSFRS-R total score for each visit will be derived from the sum of 12 items²
For the item 5 “Eating disorder,” either the item (a) or (b) will be selected corresponding to subjects with or without gastrostomy respectively. The maximum total score is $4 \times 12 = 48$.
- ALSFRS-R domains Score. The following subdomain will be calculated for each visit as well as the change from baseline to week 48.
 - Bulbar function = total of items 1 to 3
 - Limb function = total of items 4 to 9
 - Fine motor function = total of items 4 to 6
 - Gross motor function = total of items 7 to 9
 - Respiratory function = total of items 10 to 12

8.4.2.7.1. Change from screening and baseline in %Forced Vital Capacity (%FVC) at Week 24 and 48

FVC measurements will be conducted in clinic at around the same time of day where possible with the subject in sitting upright position. Subjects should make at least 3 attempts to generate acceptable and reproducible FVC data. The best value will be selected and will be recorded in the eCRF.

8.4.2.7.2. Change from baseline in Body Weight at weeks 4, 8, 12, 24, 36 and 48

Body weight will be recorded in pounds or kilograms.

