#### 17.4.5.4 Efficacy Analyses for Key Secondary Efficacy Endpoints

The following key secondary endpoints will be inferentially analyzed in the following specified order to maintain the overall Type I error. Endpoints with continuous values will be analyzed using the same method (MMRM) as for the primary efficacy endpoint. Time to death, tracheostomy, or permanent assisted mechanical ventilation (≥23 hours/day) will be analyzed using Kaplan-Meier estimates and 95% CIs. The comparison between Treatment Group 2 versus Treatment Group 1 will be performed using the log rank test. Subjects without any events during treatment will be right censored at the date of last study visit.

- 1. Change from baseline in % SVC to Week 48
- 2. Change from baseline in ALSAQ40 to Week 48
- 3. Time to death, tracheostomy, or permanent assisted mechanical ventilation (>23 hours/day)
- 4. Time to death or permanent assisted mechanical ventilation (≥23 hours/day)
- 5. Time to death

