2. INTRODUCTION

This statistical analysis plan (SAP) is based on the final global protocol (v5.0) dated 22-Sep-2022. The plan covers statistical analysis, tabulations and listings of the study data to evaluate and compare the efficacy, safety and tolerability of Oral edaravone 105 mg administered once daily to Oral edaravone 105 mg administered in cycles of ‘on/off’¹ in subjects with ALS over 48 weeks. The structure and content of this SAP provides sufficient details to meet the requirements identified by the FDA and International Conference on Harmonization of Technical Requirements for Registration of Pharmaceuticals for Human Use (ICH): E9 Guidance on Statistical Principles in Clinical Trials. All work planned and reported for this SAP will follow internationally accepted guidelines, published by the American Statistical Association, and the Royal Statistical Society, for statistical practice.

¹ 14 days, followed by placebo for 14 days and subsequently, repeat oral edaravone 105 mg administered for 10 days followed by placebo for 18 days

Statistical Analysis Plan
Protocol No. MT-1186-A02

Mitsubishi Tanabe Pharma America, Inc.

The following documents were reviewed in preparation of this SAP:

- Clinical Study Protocol MT-1186-A02 Version 5.0
- Case report form (CRF) for MT-1186-A02
- Standard Operating Procedure (SOP) GLB-BST-SOP002 for Statistical Analysis Plan
- ICH E9 Guidance on Statistical Principles for Clinical Trials.
- ICH E3 Structure and Content of Clinical Study Reports (CSRs)
- ICH E14 (may, 2005) clinical evaluation of QT/QTC interval prolongation

Any statistical analysis details described in this document supersede the description of statistical analysis in the protocol. In case of major differences, e.g. changes in the analysis related to the primary endpoint, a protocol amendment will be considered. The SAP may be updated during the study conduct and will be finalized before final database lock. Any deviations from the planned analysis will be described and justified in the CSR.

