9.2.1.4.3. Time to death, tracheostomy, or permanent assisted mechanical ventilation

(≥ 23 hours/day):

The third Key secondary endpoint is time to death, tracheostomy, or permanent assisted mechanical ventilation (≥ 23 hours/day). The analysis of this endpoint will be performed using all randomized analysis set. All available time to event data regardless of use of additional/new AMX0035 treatment (ICE1) drug and all available time to event regardless of early discontinuation (ICE2) will be included. The time to first onset (TIMETO1) of death, tracheostomy or permanent assisted mechanical ventilation will be analyzed using SAS LIFETEST procedure and the comparison between oral edaravone 105 mg daily versus oral edaravone 105 mg on/off regimen will be performed using the log rank test. This endpoint will be summarized using the number of events and percentage and displayed by Kaplan-Meier estimates with 95% CI stratified by treatment group. The decomposition of each event will be descriptively summarized.

The SAS code planned for the analysis is outlined below.

[REDACTED]

The following analyses will be used as sensitivity for the above log rank test:

- 1) Cox proportional hazard regression model will be employed for time to death, tracheostomy, or permanent assisted mechanical ventilation (TIMETO1) with terms for treatment (TREAT) as explanatory variable and baseline ALSFRS-R score (BASE), randomization strata of ALSFRS-R rate of decline (DR) score during the screening period (2 levels strata of -1,-2 or -3,-4) and geographical region - GR (3 levels strata of Europe, America or Asia Pacific) as covariates. The following SAS code will be used:

[REDACTED]

Statistical Analysis Plan Protocol No. MT-1186-A02

Mitsubishi Tanabe Pharma America, Inc.

a) The adequacy of the proportional hazards assumption will be confirmed by including a time dependent covariate of edaravone 105 mg once daily (as dummy variable) by log (time) interaction (TREAT0T) in the primary analysis model and testing it in 5% level. The following SAS code will be used:

A large rectangular area of the document has been completely blacked out, obscuring several lines of text.

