11. CHANGE FROM THE PROTOCOL

- The number and percentage of subjects with abnormal physical examinations by body system will not be summarized at each visit. This is because physical examination is measured only whether a physical examination or body system evaluation is performed or not. If any significant abnormality started, it will be record in medical history or AE.
- The FAS flag definition will be changed from “all randomized subjects who received at least 1 dose of study medication and had any efficacy data collected after randomization” to “all randomized subjects who received at least 1 dose of study medication” because all randomized subjects who randomized and received at least 1 dose of study medication should be analyzed regardless of post baseline efficacy data in order to estimate treatment effect properly.

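### SAP 8.4.2.4 gives two different censoring dates for the time-to-event key secondary endpoints, and one of them makes time at risk depend on the later outcome

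*SAP*

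**What the plan says.** SAP 8.4.2.4 defines time to death, tracheostomy or permanent assisted ventilation. Sections 8.4.2.5 and 8.4.2.6 reuse the derivation for the other two time-to-event endpoints, so it governs H04, H05 and H06.

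- **Events** count if observed "any time up to the last observed visit date when week 48 data base is locked". SAP 9.2.1.4.3 adds that "all available time to event regardless of early discontinuation (ICE2) will be included", and 9.2.1.4.4 and 9.2.1.4.5 say the same for H05 and H06.
- **Censoring, text:** "a right censoring will be performed for each subject at the last observed date of treatment".
- **Censoring, formula in the same bullet:** "Last observed Date - Randomization date +1".
- **Censoring, Protocol 17.4.5.4:** "Subjects without any events during treatment will be right censored at the date of last study visit".
- **Precedence:** "Any statistical analysis details described in this document supersede the description of statistical analysis in the protocol" (SAP section 2). SAP section 11 lists two changes from the protocol, on physical examinations and on the FAS ("The FAS flag definition will be changed from" and what follows). Neither concerns censoring.
- **Analysis set:** "The analysis of this endpoint will be performed using all randomized analysis set".
- **Follow-up:** under the time-to-event footnote of SAP Table 1, subjects who stop treatment are telephoned at Weeks 24, 36 and 48. Section 8.4.2.4 has the results and dates recorded in the eCRF.

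For the primary endpoint, the visible CAFS scoring text in 8.4.2.1 counts anyone who discontinues early, or has no Week 48 ALSFRS-R, as alive at Week 48. The notes closing SAP 3.2.1 and 3.2.2 count deaths after early discontinuation.

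**The concern.** The two SAP dates differ for every subject who stops treatment and is then followed. Under the treatment wording, a subject who stops at Week 10 and dies at Week 40 contributes 40 weeks at risk. One who stops at Week 10 and is known event-free at Week 48 contributes only 10. Risk-set membership after discontinuation then depends on what happens later, so the censoring is informative by construction. The risk set is too small and each arm's Kaplan-Meier event risk is overstated. If discontinuation differs between arms, the log-rank test and hazard ratio are biased too.

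The treatment wording also supplies no date for a subject who is randomized, never dosed and event-free, although the analysis uses all randomized subjects.

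The CAFS point is smaller. A programmer who followed the 8.4.2.1 sentence and not the two notes would rank a subject who died after discontinuing among the survivors in the primary analysis.

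**Working it through.** **1. The plan's own figure.** SAP 4.2 gives 78% power with 190 per group, HR 0.3, 90% control survival at Week 48 and a two-sided 5% log-rank test. Test-arm survival is 0.90^0.3 = 0.969. Expected events are 190 × 0.100 + 190 × 0.0311 = 19.0 + 5.9 = 24.9. Freedman: z = √24.9 × (1 − 0.3)/(1 + 0.3) − 1.960 = 2.687 − 1.960 = 0.727, giving 76.7%. A two-proportion calculation gives 77.6% and a simulated log-rank test 79.6%. So 78% reproduces with everyone followed for 48 weeks. It does not reveal the intended censoring date, because Schoenfeld's formula with 30% dropout (21.0 events) gives 78.8%.

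**2. Kaplan-Meier bias under the treatment wording.** Assumptions: constant hazard; discontinuation uniform over 48 weeks and independent of events; a share *a* of discontinued subjects followed by telephone. The 10% risk is the SAP 4.2 planning rate. The 5% is the death percentage that triggers the CAFS endpoint (19/380), used as a guide for H06. The 30% is the dropout rate SAP 4.2 assumes for ALSFRS-R.

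Let u = t/48, S(u) = (1 − risk)^u, G(u) = 1 − p·u, λ = −ln(1 − risk).

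- Event density, both rules: λS(u)[G + a(1 − G)]
- At risk, treatment wording: S·G + a[S(u) − S(1)](1 − G)
- At risk, last date known event-free: S[G + a(1 − G)], which returns the true hazard λ

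For risk 10%, p = 0.30, a = 1, λ = 0.1054, the apparent hazard is:

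- u = 0: 0.1054
- u = 0.5: 0.1054 × 0.9487/(0.9487 × 0.85 + 0.0487 × 0.15) = 0.1228
- u = 1: 0.1054 × 0.90/(0.90 × 0.70) = 0.1505

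Simpson's rule: (0.1054 + 4 × 0.1228 + 0.1505)/6 = 0.1245, and 1 − e^(−0.1245) = 11.7%.

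| True risk | a = 1 | a = 0.5 |
|---|---|---|
| 10.0% | 11.7% | 10.9% |
| 5.0% | 5.9% | 5.45% |

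**3. Effect on the comparison under no treatment difference.** Large-sample Cox HR from the same quantities; rejection from 20,000 simulated log-rank tests per setting (190 per arm, simulation SE about 0.16 points), treatment wording against corrected rule.

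| Discontinuation | True risk | Null HR, a = 1 (a = 0.5) | Rejection, a = 1 | Rejection, a = 0.5 |
|---|---|---|---|---|
| 30/30 | 10% | 1.00 (1.00) | 4.7% vs 4.9% | not given |
| 35/25 | 10% | 1.06 (1.03) | 5.4% vs 5.1% | not given |
| 40/20 | 10% | 1.13 (1.07) | 6.6% vs 5.2% | 5.5% vs 5.2% |
| 40/20 | 5% | 1.13 (1.07) | 5.9% vs 4.8% | 5.2% vs 4.9% |

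Repeat simulations at 40/20 with full ascertainment and 10% risk gave 6.0% to 6.7% under the treatment wording.

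**4. CAFS, if the sentence were followed against the notes.** N = 380 with 19 deaths, which rank 10th on average. A death recoded as a survivor joins 362 survivors above 18 deaths. At the survivors' 10th percentile, 25th percentile or median it ranks 18.5 + 36.2 = 54.7, 18.5 + 90.5 = 109.0, or 18.5 + 181 = 199.5. The arm mean moves by (rank − 10)/190 = 0.24, 0.52 or 1.00. The SE without covariates is √(380 × 381/12 × 2/190) = 11.27. A result at p = 0.050 becomes 0.052, 0.056 or 0.061 for one net miscoded control-arm death, and 0.064, 0.084 or 0.129 for five. The number of such deaths is not stated.

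**The case against.** The best defence is that the SAP's intent can be inferred. The third date belongs to the protocol, which the SAP overrides, so the live conflict is two words of text against the formula that computes the variable. The formula is not limited to treatment, the analysis sections include data after discontinuation, and call dates are in the eCRF. Table 1 labels the scheduled telephone contacts as visits, so the protocol's date may even coincide with the formula's. A programmer who follows the formula produces no bias. Randomization and first dose fall on the same Day 1 visit, so never-dosed subjects should be few. The test moves noticeably only under an assumed 40/20 split that no document supports. Tracheostomy and permanent ventilation are themselves withdrawal criteria (Protocol 9.6), so for H04 and H05 fewer events fall after discontinuation than the model assumes. On CAFS, the notes and the ranking rules settle the intent, and neighbouring text is redacted.

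Most of this stands, and it limits the size of the problem. The H04 and H05 figures are upper illustrations, and the CAFS point is a reconciliation, not a plan to ignore deaths. It does not remove the contradiction. The SAP never says that its two phrases mean the same thing, and the event window uses yet another term. The explicit rule in the text is the faulty one. The Kaplan-Meier overstatement also needs no imbalance between arms.

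**Conclusion.** The concern holds. SAP 8.4.2.4 states two censoring dates that cannot both be applied to subjects followed after treatment, and the one in the text is wrong alongside an event rule that ignores discontinuation. The surest consequence is on the reported Kaplan-Meier estimates: up to 1.7 percentage points at 10% risk and 0.9 points at 5%, given 30% uniform, independent discontinuation and full telephone ascertainment, and about half that at 50% ascertainment. The tests are affected only if discontinuation differs by arm, which is not reported; the effect is negligible at 35/25 and modest at 40/20. H04 to H06 are the last three steps of the fixed sequence, which further limits the inferential consequence. This should be fixed before programming. The CAFS wording is minor but belongs in the same revision because it touches the primary endpoint.

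**What to change.** 1. In SAP 8.4.2.4, and so in 8.4.2.5 and 8.4.2.6, censor at the last date the subject is known to be event-free from any contact, including the Week 24, 36 and 48 calls. Make text and formula identical, and apply one common Week 48 cut-off to events and censoring. State the date used for randomized subjects who were never dosed.
2. List the departure from Protocol 17.4.5.4 in SAP section 11.
3. In 8.4.2.1, restrict the alive-at-Week-48 rule to participants not known to have died by the Week 48 cut-off, and cross-refer to 3.2.1. State the cut-off day, as 9.2.1.5.6 does for Week 24 (Day 211, the end of that window). The same convention would give Day 379 from Table 5. If redacted text already covers this, a cross-reference is enough.

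The cost is SAP wording and derivation code. No new data are needed, because call results and dates are already recorded in the eCRF.
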